6.5.1 Compliance

Compliance of administration of the trial drug by the patient need not be monitored, because the drug will always be administered by the attending physician (member of the trial group) or caregiver on the ICU or checked by these persons and documented in the medical record.

6.6 Instructions for the control group without albumin

Patients in the control group are treated according to standard practice with any crystalloid solution as volume replacement therapy of first choice. In patients of the control group, albumin administration should not be considered. If, however, according to the judgment of the treating physician (member of the trial group), it is necessary to consider albumin replacement therapy for clinical reasons, this can of course be done. This may be the case if, for example, the serum albumin level decreases below 15 g/l. The following factors should be considered:

- Active substance of the administered product: Albumin, but do not use the product provided for use in the trial!
- Application: intravenous, following the instructions in the respective drug information brochure
- Dosage: as low as possible
- Documentation of the drug

The administration of albumin to a participant in the control group leads to exclusion of this patient from the per-protocol analysis.

6.7 Permitted concomitant medication, concomitant therapies

There are no restrictions to concomitant medication and therapies during the trial. Concomitant medication and therapies must be documented.

6.8 Further treatment of participants after the end of participation

Specific aftercare or follow-up is not needed after a maximum of 28 study days of administration of the trial drug to patients in the albumin group, or after discharge from the ICU or withdrawal of consent in both groups. Treatment with the trial drug is an intensive care measure that is of no consequence to subsequent medical care. The administration of

Stary pro

human albumin 200 g/l solution for infusion as a trial drug while participating in a clinical trial will be communicated to the treating physician in the discharge report.

ZKSJ0112 ARISS

Study protocol, Version 3.0

7. Start, course and end of the clinical trial/study visits

General remarks:

- Patients in the participating ICUs will be screened during the ICU stay to see whether they fullfil the inclusion criteria and do not meet exclusion criteria. Informed consent for participation in the trial will be sought from all patients ≥18 years of age with septic shock.
- General treatment of patients participating in the clinical trial will follow usual practice for this condition and will be consistent with current guidelines for the treatment of such patients (25).
- Crystalloids will be administered in both groups according to usual practice.
- Antimicrobial therapy should be performed according to PK/PD principles. Increasing the dosage of antimicrobial agents with high protein binding capacity should be weighed in patients with hypoalbuminemia.
- Collection of microbiological samples as part of the primary diagnosis of sepsis or of developing infections is at the discretion of the treating physician and is not trial-related. Nonetheless, microbiologic diagnostics should be sought, especially in the form of blood cultures, before starting antimicrobial therapy.
- Trial-related measures may only take place after consent!
- A patient may be included in the trial only if all the inclusion criteria (including negative pregnancy test) are met and all exclusion criteria are absent.
- In the case of a woman of childbearing potential, a pregnancy test should be carried out after obtaining informed consent. Before the result is available, the patient must not be randomised. If the pregnancy test is positive, participation in the clinical trial for the patient will end promptly.
- A study day is defined by the treatment day according to the routine practice of the respective trial centre. A study day changes when a new daily data record sheet is created in the trial centre. The 1st day after randomisation (1st study day) is the 1st full treatment day (24 h) after the day of randomisation.

7.1 Screening and 24-h period before randomisation

- Obtaining written informed consent or confirming the urgency of participating in the clinical trial with possible patient benefit by an independent consultant or other procedures established in the trial centre to include patients who are unable to provide informed consent
- Checking the inclusion and exclusion criteria (including pregnancy test (blood or urine) for women of childbearing age)
- Recording the time of onset of septic shock
- Collection of basic data (sex, age, weight, height, time of hospital admission, time of ICU admission, type of admission, referring facility prior to transfer to the ICU, etc.)
- Documentation of primary or secondary admission diagnoses
- Documentation of concomitant diseases present on admission to the ICU
- Collection of data on infection, microbiology and anti-infective therapy
- Collection of raw data for the calculation of APACHE II, SAPS II, and SOFA scores from the routine laboratory requests (not for study purposes) from the 24-h period before randomisation (data from ICU or normal ward) (see Appendix)
- Assessment of concomitant medication (catecholamines, inotropes, diuretics, fluid therapy including transfusion, adjunctive sepsis therapy) from the 24-h period prior to randomization
- Recording of intensive care interventions (intubation (ITN), central venous catheter (CVC), arterial catheter (AC), renal replacement therapy (RRT), ventilation, extracorporeal

membrane oxygenation (ECMO), haemodynamic monitoring during the 24-h period before randomisation

 Recording clinical parameters (body temperature, respiratory haemodynamic parameters (SAP, MAP, DAP, CVP, CO) from the 24-h period before randomisation

7.2 Time of randomisation

Randomisation leads to the assignment of a participant to the albumin group or to the control group without albumin.

The randomisation day is defined as the treatment day on which the randomisation takes place. It ends when a new daily treatment sheet is created.

Randomisation must be performed within two hours of the written informed consent or confirmation of urgency of participation in the clinical trial with possible benefit to the patient by an independent consultant or other procedures established in the trial centre to include patients who are unable to provide informed consent

The randomisation is carried out by an automated internet-based service, which is provided by the Centre for Clinical Studies Jena (ZKS). The group assignment is retrieved via a validated electronic tool (PaRANDies) by the respective trial centre. The group assignment of the patient must be documented (patient record, e-CRF). Each participant will receive a randomisation number.

- Collection of data on infection, microbiology and anti-infective therapy
- Recording of clinical parameters (body temperature, respiratory haemodynamic parameters) at the time of randomisation (+/- 1 hour)
- · Recording of concomitant medication (catecholamines, inotropes, diuretics, fluid therapy including transfusion, adjunctive sepsis therapy) at the time of randomisation (+/- 1 hour)
- Collection of routine data from the laboratory (not trial-related), performed in the 24-h period before randomisation: haemoglobin, creatinine, bilirubin, C-reactive protein, procalcitonin, leucocytes, platelets, lactate, arterial blood gas analysis (PaCO2, PaO2, FiO2, SO2, pH, ScO2)
- Recording of intensive care interventions (ITN, CVC, AC, RRT, ventilation, ECMO, haemodynamic monitoring) at the time of randomisation (+/- 1 hour)
- Start capturing AEs, SAEs, sepsis-related clinical events

7.3 Time period until 2 h after randomisation

- Collection of data on infection, microbiology and anti-infective therapy
- Capture of AEs, SAEs, sepsis-related clinical events
- Procedure according to group allocation:

Albumin group:

- 1. Blood sampling to determine serum albumin concentration within 2 hours after randomisation
- 2. Starting dose of the trial product within 6-24 h after the onset of septic shock: 60 g Human albumin 20% (200 g/l solution for infusions) over 2-3 h
- 3. Data collection trial drug on administration (continuous collection).

Control group without albumin:

- 1. Blood sampling to determine serum albumin concentration within 2 hours after randomisation
- 2. Treatment according to usual practice with crystalloids as the first-choice fluid treatment.

Study protocol, Version 3.0

7.4 Trial visit at 6 h after randomisation

- Collection of data on infection, microbiology and anti-infective therapy
- Recording of co-medication with catecholamines and inotropes at this specific time-point (+/- 1 hour)
- Recording of concomitant medication with diuretics, fluid therapy including transfusion, adjunctive sepsis therapy) during the past 6 h
- Recording of clinical parameters (respiratory frequency, haemodynamic parameters) at this specific time point (+/- 1 hour)
- Collection of routine laboratory data (not trial-related) at this specific time point (+/- 1 hour): haemoglobin, lactate, arterial blood gas analysis (PaCO2, PaO2, FiO2, SO2, pH, ScO2)
- Recording of intensive care interventions (ITN, RRT, ECMO, mechanical ventilation, haemodynamic monitoring) from the previous 6 hours
- Capturing of AEs/SAEs and sepsis-related clinical events (continuous)
- Recording vital status (alive/dead)
- Data collection about administration of the trial drug (continuous), including information on the administered dose, interruption or discontinuation of the dose if necessary

7.5 Trial visits on trial days 1 to 28 after randomisation

These visits should only be performed if the patient is still being treated in the ICU.

- Blood sampling to determine the serum albumin concentration, including recording the time of blood sampling
- Blood samples for serum albumin concentration determination may be performed as part of the routine blood sampling procedure at the respective trial centre, provided that they are taken between 4:00 and 9:00 in the morning.
- Collection of data on infection, microbiology and anti-infective therapy
- Recording of the raw data for calculation of the SOFA score on the respective study day from the routine laboratory results (not for trial purposes); the "worst" daily value should be recorded
- Recording of concomitant medication with catecholamines and inotropes, diuretics, fluid therapy (including transfusion therapy, adjunctive sepsis therapy) on the respective trial day
- Recording of intensive care interventions (ITN, CIC, AC, RRT, mechanical ventilation, ECMO, haemodynamic monitoring) on the respective trial day
- Recording the amount of enteral and parentral fluid adminstration on the trial day
- Collection of routine laboratory data (not trial-related), taken between 4:00 9:00 in the morning: haemoglobin, creatinine, bilirubin, C-reactive protein, procalcitonin, leucocytes, platelets, lactate, arterial blood gas analysis (PaCO2, PaO2, FiO2, SO2, pH, ScO2)
- Recording of clinical parameters (body temperature, respiratory frequency and haemodynamic parameters), 24 h urinary output, other fluid loss on the trial day
- Capturing of AEs/SAEs and sepsis-related clinical events (continuous)
- Recording of vital status (live / dead)
- Albumin group: administration of the trial drug according to serum albumin concentration, dose adjustment according to the given scheme
- Data collection regarding administration of the trial drug (continuous), including information on the administered dose, interruption or discontinuation of the dose if necessary Note: After administration of the trial drug on day 28, no further doses are given.

7.5.1 Data collection at hospital discharge or at the end of the study

Data will be collected from participants at one of the following time points, whichever comes first:

ZKSJ0112 ARISS

- Discharge from the hospital before or on trial day 28
- Discharge from the hospital up to and including trial day 90
- Trial day 90 reached in the hospital (regular end of study)
- Early termination of the clinical trial as described in 7.6

Data collection:

- Recorde data on ongoing SAEs and serious sepsis-related clinical events
- Vital status (alive/dead): if applicable date of death and cause of death; if applicable, recording of "end of life" decisions, stay after discharge
- ICU length of stay (of the first ICU stay after study participation)
- Hospital length of stay (first hospital stay after study participation)

If the patient is discharged from the ICU or the hospital during the 90-day observation period, this time will be defined as the endpoint for determining the ICU length of stay and/or hospital stay. If the patient returns to the ICU or hospital within the 90 days, this is no longer relevant for the collection of trial endpoints.

7.5.2 Data collection at trial days 28, 60, and 90 after randomisation

At these time points, data will be collected on the primary and secondary "mortality" outcomes. If the patient has already left the hospital before these time points, contact with the patient, his quardian or legal representative will take place to collect the required data.

- Vital status (alive/dead): if applicable date of death and cause of death; if applicable, recording of "end of life" decisions, stay after discharge
- · Verification of the documentation of SAEs already detected and serious sepsis-related clinical events, possibly AEs, which are "ongoing" at the respective time point

7.6 Premature end of the participation of a patient in the clinical trial

Participation of a patient in the clinical trial may be prematurely terminated for the following circumstances:

- Death of the participant
- Failure to obtain consent to the continuation of the clinical trial by a guardian or a legal representative according to the respective time windows in patients who participated after confirmation of the urgency of participation in the clinical trial by an independent consultant or other procedures, established in the trial centre to include patients who are unable to provide informed consent
- Refusal to continue the clinical trial by formerly incapacitated patients who have regained their ability to consent
- Abort at own request, withdrawal of consent to participate in the clinical trial
- Occurrence of any of the circumstances described in 7.7.2 and 7.7.3

Termination of participation in the trial, drop-out at own request

Participation in the clinical trial is voluntary. Each participant has the right, at any time and without stating reasons, to withdraw his/her consent prematurely from the clinical trial without incurring disadvantages for his/her further medical treatment. Withdrawal of consent leads to termination of the clinical trial in the patient.

Study protocol, Version 3.0

- The patient, his/her guardian or legal representative will be asked to give the reason for his decision, but without any obligation to do so.
- The patient, his/her guardian or legal representative will be informed that no further studyrelated measures will be carried out, but that the stored data may continue to be used, as far as is necessary to determine the effects of the intervention and to ensure that patient's interests will not be affected.
- The patient, his/her guardian or legal representative should be asked to provide the data requested at the end of the study.
- The patient's observations and documentation related to the clinical trial will be terminated.
- The SpB must be informed of the termination of participation at own request.

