1.1 Overview of the clinical trial

	Randomised controlled multicentre study of albumin	
Title of the trial	replacement therapy in septic shock	
Trial Acronym	ARISS-Study	
Sponsor according to AMG	Friedrich Schiller University Jena	
Sponsor's legal representative (SpB) and principal investigator (LKP)	[name]. [name] Universitätsklinikum Jena Klinik für Anästhesiologie und Intensivmedizin [name] [contact] [contact] E-Mail: [contact]	
EudraCT Number	2018-001874-89	
Study population	Female and male patients ≥ 18 years treated in the intensive care unit (ICU) within 24 hours of septic shock diagnosis	
Study phase	III b	
Trial design	Prospective, multicentre, randomised, controlled, parallel- grouped, open-label, interventional clinical trial according to the German Medicinal Products Act	
Primary target: To investigate whether albumin administration and maintenance of serum albumin concentrations of a 30 g/l in the ICU for up to 28 days after the onset of shock, will reduce total 90-day mortality compared volume replacement therapy without albumin Secondary targets: - To investigate whether albumin administration at maintenance of serum albumin concentrations of 30 g/l in the ICU for up to 28 days after the onset septic shock would influence ICU, hospital, 28-a day mortality rates, rates of organ dysfunction/far assessed by the SOFA score, ICU/hospital length stay, ventilator and vasopressor-free days. - Cost-benefit analysis of volume replacement the		
Primary outcome (primary	from ICU admission until maximum day 28 Primary outcome: 90-day all-cause mortality	
end-point)		
Secondary outcome	Secondary outcomes:	
(secondary end-point)	 - 28- and 60-day mortality, mortality rates in the ICU and during hospitalization, organ dysfunction/failure as assessed by the SOFA score, ICU and hospital length of stay, ventilator and vasopressor free days. 	

ARISS
EudraCT-Nr.: 2018-001874-89
ZKSJ0112_ARISS
UNIVERSITATS
KLINIKUM
Jena

Sample size	 Cost-benefit parameters of volume replacement therapy (albumin, other colloids and crystalloids) Total amount of fluid of fluid administration and total fluid balance in the ICU. Safety related endpoints: Onset of AEs and SAEs, in particular anaphylactic shock, hypervolaemia, pulmonary oedema and sepsis-related clinical events Assuming a 90-day mortality of 50% in the control group without albumin and 42% in the albumin group, 1412 patients need to be evaluated (power: 80%, Chi²Test alpha

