writing. If the conversation with relatives reveals that it is likely the patient would not have wanted to participate, the patient will not be included in the clinical trial. If the patient is known to want to participate in clinical trials or if the patient's relative agrees to participation in the study (provisionally), this information will be forwarded immediately to the competent court, which will promptly appoint a legal representative. In this case, the patient will be included in the clinical trial. Subsequently, with this provisionally granted consent, the written consent of the appointed legal representative must be obtained as soon as possible. If the patient dies before the legal representative has been appointed or consented, the patient should not be excluded from the analysis. If SAEs have occurred, they must be pursued further in accordance with the relevant requirements.

In this case, the trial centers should adopt the locally established procedure for including patients unable to consent and follow the recommendations of the local ethics committee. The appropriate procedure must be documented.

If, for example, the appointment of a legal representative (supervisor, health care task designation) is required, this must be done as soon as possible (at the latest, however, within 72 hours).

Written consent to the clinical trial or its continuation by the legal representative must be obtained. If this does not occur within a maximum of 72 hours of setting up the legal representation, or if the legal representative refuses (further) participation in the study, the patient will not be included in the clinical trial or his / her participation in the clinical trial will be terminated.

If SAEs have occurred before the decision of the legal representative, theses will be prosecuted in accordance with the applicable requirements.

If the patient dies before the legal representative has been appointed or has decided to participate, this must be documented accordingly in the eCRF.

The "independent medical consultant procedure"

In this procedure, confirmation of the urgency of participation in the clinical trial and possible benefit to the patient may be obtained by an independent consultant and the patient subsequently becomes a participant in the clinical trial.

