9.8 Privacy and privacy statement

This clinical trial will serve a scientific goal of considerable clinical relevance. To achieve this goal, it is necessary to collect and process medical data from individual patients. Data collection will take place in the involved trial centres. All collected medical data will be entered in the trial centres with the aid of a computer-aided online data collection system and transmitted directly to the documentation centre based at the ZKS of the Jena University Hospital. Name-related identification of individual patients by the documentation centre is not required at any time during the clinical trial. During data collection and data processing, therefore, all necessary measures will be taken at the earliest possible date in order to establish de facto anonymisation.

Transfer of patient-related medical data from the trial centres to the documentation centre will be carried out using a pseudonym. No features will be transferred that enable immediate identification of specific patients by the documentation centre. However, to conduct queries within the framework of the ongoing monitoring of the quality of documentation, it is necessary for the documentation centre to assign pseudonyms to specific trial centres.

In the case of revocation of consent, no further data will be collected. Data already collected will not be deleted.

The data entry, processing and evaluation carried out at ZKS Jena comply with the provisions of the Data Protection Act. Only employees of ZKS Jena will have access to all clinical trial data. These persons are sworn to secrecy. The data will be protected against unauthorised access.

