10.3 Audits and inspections

Within the scope of quality assurance, the SpB can have an independent audit conducted at any time in the participating institutions. In this case, the investigator or the participating institution will grant the auditor access to all documents necessary for the audit.

Inspections as part of the monitoring of ongoing or already completed clinical trials are carried out by the competent authority in accordance with § 64 (1) of the AMG (28). The inspection conducted by the competent authority shall be carried out in accordance with a written procedure and a pre-determined plan.

The SpB and all participating trial centres are committed to supporting inspections by competent authorities and, in this regard, to grant authorised persons access to the original data and documents.

Statistical methods and determination of sample 11. size

Sample size

The 90-day mortality in the control arm is estimated to be about 50% (taking into account the possible use of albumin in the control group) (4, 7, own pilot study).

For the sample size estimation, a 15% reduction in 90-day mortality is assumed, i.e., an absolute reduction of 7.5 percentage points to 42.5% (relative risk 1.18). This limit was chosen because the relatively costly albumin therapy can only be justified if there is a sufficiently clear treatment effect. This assumed effect size has the potential to affect current standard of care and international treatment guidelines and lies between the observed reduction in 90-day mortality in patients with septic shock (13%) and the assumed effect size in the ALBIOS study (23). Following the recommendation of the reviewers of the DFG application of the ARISS study, the sample size was estimated taking into account a centre variability (probably about 50 centres) in mortality of patients in the control arm of the study between 40% and 60% and a risk reduction between 12% and 18% (coincidentally uniform).

A Mantel-Haenszel Chi² test at a two-tailed significance level of 0.05 with a power of 80% requires 1412 patients to be analysed, 706 per arm, to demonstrate such an effect.

This case number estimate can be considered conservative for the planned analysis (nonlinear mixed model taking into account random centre effects).

The case number estimation was performed using SAS 9.4 (SAS Institute Inc., Cary, NC, USA).

Dropout Rate:

Approximately 15%, through

- "loss to follow up" until day 90

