- refusal to continue in the clinical trial by incapacitated patients who regain their capacity to consent. and
- failure to consent to the continuation of the clinical trial by the guardian or the legal representative within the respective time windows in patients who became participants after confirmation of the urgency of participation in the clinical trial by an independent consultant or other procedures, established in the trial centres to include patients who are aunable to provide informed consent (VISEP 10.5%). MaxSep 8.2%) (25, 26).

Assuming a dropout rate of 15%, 1662 patients need to be randomised.

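### Protocol sections 7.5.1, 7.6 and 9.8 conflict on what is collected after consent ends, so day-90 vital status, the primary endpoint, may be lost in patients who are alive when they leave

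*Protocol*

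**What the plan says.** **After withdrawal.** Protocol section 7.6, under drop-out at own request, says that the patient or representative "should be asked to provide the data requested at the end of the study". The next bullet reads: "The patient's observations and documentation related to the clinical trial will be terminated". Section 9.8 adds: "In the case of revocation of consent, no further data will be collected".

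**At early termination.** Section 7.5.1 makes early termination under 7.6 a data-collection point that includes vital status. It applies at whichever listed time comes first, so it records status on the day of leaving. Section 7.5.2 plans contacts at days 28, 60 and 90, but does not say whether they apply after withdrawal.

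**Missing deferred consent.** Sections 5.2.2 and 7.6 end participation when the representative refuses or does not consent within the time window, and 7.6 also when a patient who regains capacity refuses to continue. Under 5.2.2, SAEs that have already occurred are still pursued. For patients without a guardian, 5.2.2 says: "If the patient dies before the legal representative has been appointed or consented, the patient should not be excluded from the analysis". For the independent-consultant route it says only that such a death is documented in the eCRF.

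**Planned loss.** The dropout paragraph of section 11.1 allows about 15%. It lists loss to follow-up, "refusal to continue in the clinical trial by incapacitated patients who regain their capacity to consent", and missing consent from the representative.

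**Analysis.** Protocol section 11.3.2 adds multiple imputation as a sensitivity analysis if more than 10% of day-90 mortality data are missing. SAP section 5.1 replaces no missing values other than short gaps in the GCS, and says that missing day-90 mortality is taken into account in the Kaplan-Meier analysis.

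**The concern.** A site that follows 7.6 and 9.8 cannot tell whether a day-90 call is allowed after withdrawal. If it reads the terminating bullet and 9.8 literally, the primary endpoint is missing for that patient, although only alive or dead at day 90 is needed.

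The loss is not obviously neutral. A patient must be alive to withdraw, to regain capacity and refuse, or to pass the consent window without a signature. A patient in the no-guardian route who dies before that point is counted as a death. Early deaths are thus kept while some living patients leave without a known outcome. If those who leave have lower 90-day mortality than the rest, observed mortality is too high in both arms. If the share leaving also differs by arm, which is possible because treatment is open (Protocol section 11.2), the treatment comparison is biased.

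The primary model in SAP section 6.6 is for a binary outcome. A patient without a day-90 outcome adds nothing to it, even though the FAS definition in SAP section 2.1 keeps that patient in the analysis set.

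**Working it through.** **1. The plan's own numbers.** Inputs from Protocol section 11.1: 50% against 42.5% mortality, two-sided alpha 0.05, power 80%, 706 per arm (1412), 15% dropout, 1662 randomised.

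- Per arm, n = [1.960 × √(2 × 0.4625 × 0.5375) + 0.842 × √(0.5 × 0.5 + 0.425 × 0.575)]² / 0.075² = 693, so 1386 in total (1438 with continuity correction). The stated 1412 lies between these.
- A simulated Mantel-Haenszel test with the stated centre variability gives 80.4% power at 706 per arm.
- 1412 / 0.85 = 1661.2, rounded up to 1662.

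The synopsis prints 42% for the albumin arm. That gives 1218 rather than 1412, so 42.5% is used here.

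**2. How many patients.** Planned loss is 1662 − 1412 = 250. This covers ordinary loss to follow-up as well as the consent routes, and no split is given. Section 11.1 prints 10.5% and 8.2% from two earlier trials beside the missing-consent route. If those are rates for that route, it would account for 0.082 × 1662 = 136 to 0.105 × 1662 = 175 patients.

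**3. Formula.** With true mortality p in an arm, share lost d and 90-day mortality m among those lost, mortality in the patients analysed is

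(p − d × m) / (1 − d) = m + (p − m) / (1 − d).

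The documents give neither m nor d by arm. Both are assumptions below, with m the same in both arms.

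**4. A reference value for m.** In the registry of Protocol section 4.2, 62 of 1478 patients (4.2%) died or were moved within 24 hours. Suppose at most that share dies before consent is settled and that, among those still alive, leaving is unrelated to prognosis. Then survival among lost controls is 0.50 / (1 − 0.042) = 52%, so m is about 48%. If those who leave are recovering, m is lower; 10% to 30% is used for that case.

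**5. Equal loss of 15%, m = 20%.**

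- Control: (0.50 − 0.03) / 0.85 = 55.3%.
- Albumin: (0.425 − 0.03) / 0.85 = 46.5%.
- The risk ratio is 0.84 instead of 0.85 (0.85 at m = 0, 0.82 at m = 48%).
- The absolute difference is 7.5 / 0.85 = 8.8 points for any m.
- With no true effect both arms shift alike, the difference is zero and type I error stays at 5%.

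**6. Unequal loss, 18% against 12%, no true effect (50% in both arms).** The false difference is (0.50 − m) × (1/0.82 − 1/0.88) = (0.50 − m) × 0.0831. Type I error uses 831 × 0.82 and 831 × 0.88 patients.

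| m | False difference | Two-sided type I error |
|---|---|---|
| 10% | 3.3 points | 24% |
| 20% | 2.5 points | 16% |
| 30% | 1.7 points | 10% |
| 48% | 0.2 points | 5% |

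**7. Unequal loss with a true 7.5-point effect, m = 20%.** If controls lose 18% and albumin 12%, the estimate is 56.6 − 45.6 = 11.0 points. With the arms reversed it is 54.1 − 47.4 = 6.7 points.

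**8. What full ascertainment would give.** Day-90 status for all 831 per arm gives 86.6% power, against 80.7% with 706 per arm and uninformative loss.

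**The case against.** **Observation does not end altogether.** A reader might infer from the terminating bullet that it does. The documents do not support that. Section 7.5.1 records vital status at termination, and 5.2.2 still pursues SAEs. The bullet stands under drop-out at own request, so it does not expressly govern missing deferred consent. Sections 5.2.3, 6.4 and 6.5 already separate stopping the trial drug from ending follow-up. This narrows the point but does not secure day-90 status for those whose participation ends.

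**A request already exists.** Section 7.6 does ask for end-of-study data, which may be meant to include vital status. The consent pages and the eCRF discontinuation section were not available, so it cannot be said that no such item exists there. The next bullet and 9.8 still contradict the request.

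**Loss mainly of survivors is an inference.** The documents show patients alive when they leave, not alive at day 90. Missing representative consent works on 72-hour windows, so these patients leave early and may have near-average mortality. At 48% the bias in step 6 almost vanishes. This objection stands, and it is why the range runs down to 0.2 points.

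**Unequal refusal is not shown.** This also stands. The 18% and 12% are illustrative, and even unequal loss does no harm if dropout mortality matches that of the arm.

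**The analysis offers some repair.** A planned 15% loss would trigger the protocol's multiple imputation. It is only a sensitivity analysis, however, and the SAP does not carry it over. Kaplan-Meier estimates use the time a lost patient was known to be alive, but SAP section 6.7 makes them descriptive, and they too assume that leaving is unrelated to prognosis.

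**Conclusion.** The conflict between sections 7.5.1, 7.6 and 9.8 is in the text and does not depend on any assumption. As written, day-90 vital status is not secured for patients who withdraw, who refuse after regaining capacity, or whose representative refuses or does not consent in time. It may be lost; that it will be lost is not established. All these patients are alive at loss, and the no-guardian route keeps deaths before consent, so missingness can depend on outcome.

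The size is uncertain. The planned 250 is an upper limit for the consent routes, because it includes ordinary loss to follow-up. Equal loss does not damage the test and barely moves the risk ratio, though it overstates mortality in both arms and stretches the absolute difference. Material bias needs both unequal loss and dropout mortality well away from the arm's own. A reader might infer that the trial loses mainly survivors and that its estimate is therefore biased; the documents show neither. The figures for unequal loss illustrate what is at risk and do not predict it. An inexpensive correction is worth making because the item at stake is the primary endpoint and the planned analyses do not reliably recover it.

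**What to change.** 1. Reconcile Protocol sections 7.5.1, 7.6 and 9.8 so that they distinguish withdrawal from trial measures from refusal of follow-up, and say what may be collected in each case.
2. Ask each withdrawing patient or representative specifically for permission to record day-90 vital status and nothing else. Record the answer in the eCRF. The day-90 contact in section 7.5.2 can be used.
3. Where deferred consent is missing, there may be no answer to record. Collect day-90 status only where the ethics committee and applicable law permit it, not by default.

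The cost is an ethics-approved amendment to the protocol and, if needed, the consent form, plus one eCRF field if none exists. Some patients will still refuse, so some loss will remain.
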